10.4.1.4. Treatment States for AE Data

Non-serious AEs and serious AEs are to be recorded on the eCRF starting at the placebo run-in phase. Serious AEs assessed as related to study procedures or related to a GSK concomitant medication are to be recorded on the eCRF from the time a subject consents to participation in the study. AE of worsening of an on-going event will be counted once in a particular treatment state.

Treatment State	Definition
Pre-treatment	
 • For subjects with a non-missing screen failure date, if AE onset is on or before the screen failure date: AE Start Date \leq Screen Failure Date • For randomized subjects with a missing treatment start date, all AEs are considered pre-treatment • For randomized subjects with a non-missing treatment start date, if AE onset date is before treatment start date: AE Start Date $<$ Treatment Start Date
Placebo Run-In	
If AE onset date or AE worsening date is on or after placebo run-in treatment start date & on or before placebo run-in treatment stop date: Placebo Run-in Treatment Start Date \leq AE Start Date \leq Placebo Run-in Treatment Stop Date Placebo Run-in Treatment Start Date \leq AE Worsening Date \leq Placebo Run-in Treatment Stop Date AE worsening during placebo run-in will be defined relative to the maximum intensity of AE prior to placebo run-in start date. AE worsening date is the first date in the placebo run-in period, when AE intensity increased relative to the maximum intensity of the AE prior to placebo run-in start date.

Post-randomization	
If AE onset date or AE worsening date is on or after the randomization date Randomization date \leq AE Start Date Randomization date \leq AE Worsening Date AE worsening during post-randomization will be defined relative to the maximum intensity of AE prior to randomization date. AE worsening date is the first date in the post-randomization period, when AE intensity increased relative to the maximum intensity of the AE prior to randomization date.

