Treatment emergent	
If AE onset date or AE worsening date is on or after treatment start date & on or before the last non-zero dose date plus 1 day. Treatment Start Date \leq AE Start Date \leq Last Non-Zero Dose Date + 1 day Treatment Start Date \leq AE Worsening Date \leq Last Non-Zero Dose Date + 1 day AE worsening during treatment emergent will be defined relative to the maximum intensity of AE prior to randomized treatment start date. AE worsening date is the first date in the treatment emergent period, when AE intensity increased relative to the maximum intensity of the AE prior to randomized treatment start date.

Follow-up	
If AE onset date or AE worsening date is after the last non-zero dose date plus 1 day. AE Start Date $>$ Last Non-Zero Dose Date + 1 day AE Worsening Date $>$ Last Non-Zero Dose Date + 1 day AE worsening during follow-up will be defined relative to the maximum intensity of AE prior to randomized treatment start date. AE worsening date is the first date in the follow-up period, when AE intensity increased

	relative to the maximum intensity of the AE prior to randomized treatment start date.
Onset /Worsening Time Since 1 st Dose (Days)	If Treatment Start Date > AE Onset Date = AE Onset Date - Treatment Start Date If Treatment Start Date ≤ AE Onset Date = AE Onset Date - Treatment Start Date + 1 If Treatment Start Date > AE Worsening Date = AE Worsening Date - Treatment Start Date If Treatment Start Date ≤ AE Worsening Date = AE Worsening Date - Treatment Start Date + 1 Missing otherwise.
Onset/Worsening Time Since Last Dose (Days)	If Last Non-Zero Dose Date ≤ AE onset date: AE onset date – last non-zero dose date +1 If Last Non-Zero Dose Date > AE onset date: AE onset date – last non-zero dose date If Last Non-Zero Dose Date ≤ AE worsening date: AE worsening date – last non-zero dose date +1 If Last Non-Zero Dose Date > AE worsening date: AE worsening date – last non-zero dose date Missing otherwise.
Duration (Days)	AE Resolution Date – AE Onset Date/AE Worsening Date + 1
Drug-related	If relationship is marked 'YES' on eCRF or if the value is missing.

NOTES:

- AEs that occur or worsen during interruptions of randomized study treatment will be classified as treatment emergent and post-randomization.

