10.6.4.4. Adverse Events

Adverse Events
AEs of Special Interest

Adverse events of special interest are classified as follows:
 
 • Thrombosis and/or tissue ischemia secondary to excessive erythropoiesis • Cardiomyopathy • Pulmonary artery hypertension • Cancer-related mortality and tumor progression and recurrence • Esophageal and gastric erosions • Proliferative retinopathy, macular edema, choroidal neovascularization • Exacerbation of rheumatoid arthritis • Worsening of hypertension

Adverse Events

Potential AESIs will be identified through a pre-defined terms of interest process in which pre-defined lists of AE preferred terms corresponding with each AESI will be used to identify events considered to be potential AESIs. Sites will be prompted via query to complete any necessary additional information for these AESIs in the eCRF.

For the category of thrombosis and/or tissue ischemia secondary to excessive erythropoiesis, after the terms of interest list has been applied, the additional Hgb criteria described below will be applied to identify only those events that are considered to be secondary to excessive erythropoiesis as meeting the AESI definition for thrombosis and/or tissue ischemia secondary to excessive erythropoiesis.

Thrombosis and tissue ischemia events will be considered to be secondary to excessive erythropoiesis if during the window of [AE start date – 30 days, AE start date +15 days] any one of the following 3 events occurs:

- Any Hgb value \geq 13 g/dL (measured pre-dialysis)
- Hgb increase $>$ 2 g/dL over 2 weeks (+1 week)
 - Note: for programming purposes, a +1 week window is applied, corresponding to the allowable visit window, to look for increases $>$ 2 g/dL over 3 weeks
- Hgb increase $>$ 4 g/dL over 4 weeks (+1 week)
 - Note: for programming purposes, a +1 week window is applied, corresponding to the allowable visit window, to look for increases $>$ 4 g/dL over 5 weeks

To identify Hgb increases that meet the increase criterion above, all Hgb values taken within [AE start date – 58 days, AE start date + 15 days] will be identified. This corresponds to identifying Hgb values that occurred 4 weeks before the [AE start date – 30 days, AE start date +15 days] window of interest. HemoCue Hgb and central laboratory Hgb values will then be evaluated separately to identify increases, so that HemoCue and central laboratory Hgb values are not compared to each other to identify an increase.

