For HemoCue Hgb and separately for central laboratory Hgb values, if there is a Hgb value (or daily Hgb average) within the [AE start date – 30 days, AE start date +15 days] window and an earlier Hgb value (or daily Hgb average) that is within the larger [AE start date – 58 days, AE start date + 15 days] window, and the amount of time between the two Hgb values is:

- Between 1 day and 3 weeks, inclusive, then the Hgb values will be compared to determine if there has been a Hgb increase $>$ 2g/dL.
- Between 15 days and 5 weeks, inclusive, then the Hgb values will be compared to determine if there has been a Hgb increase $>$ 4g/dL.

Unscheduled Hgb values will also be used in the assessment of secondary to excessive erythropoiesis following the guidance specified in Section [10.6.3](#) for unscheduled Hgb values and

Adverse Events

multiple Hgb values on the same date.

Pre-defined Lists of AE Preferred Terms Corresponding with Each AESIThrombosis and/or tissue ischemia secondary to excessive erythropoiesis

- Narrow SMQ: Embolic and thrombotic events, arterial
- Narrow SMQ: Embolic and thrombotic events, venous
- Narrow SMQ: Embolic and thrombotic events, vessel type unspecified and mixed arterial and venous
- Broad SMQ: Thrombophlebitis
- Additional Preferred Terms:
 - Vascular access site occlusion
 - Vascular access site complication
 - Retinal vascular occlusion
 - Administration site ischaemia
 - Anterior segment ischaemia
 - Application site ischaemia
 - Biliary ischaemia
 - Bone marrow ischaemia
 - Brain stem ischaemia
 - Catheter site ischaemia
 - Cerebellar ischaemia
 - Cerebral ischaemia
 - ECG signs of myocardial ischaemia
 - Gastrointestinal ischaemia
 - Graft ischaemia
 - Hepatic ischaemia
 - Implant site ischaemia
 - Infusion site ischaemia
 - Injection site ischaemia
 - Intestinal ischaemia
 - Ischaemia
 - Macular ischaemia
 - Medical device site ischaemia
 - Myocardial ischaemia
 - Peripheral ischaemia
 - Renal ischaemia
 - Retinal ischaemia
 - Spinal cord ischaemia
 - Stoma site ischaemia
 - Subendocardial ischaemia
 - Uterine ischaemia
 - Vaccination site ischaemia
 - Vestibular ischaemia
 - Cerebral small vessel ischaemic disease
 - Colitis ischaemic
 - Delayed ischaemic neurological deficit
 - Hypoxic-ischaemic encephalopathy
 - Ischaemic cardiomyopathy
 - Ischaemic cerebral infarction
 - Ischaemic contracture of the left ventricle
 - Ischaemic enteritis
 - Ischaemic gastritis
 - Ischaemic heart disease prophylaxis

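### For thrombosis and ischemia AEs that are treatment emergent only through worsening, the Hgb test for excessive erythropoiesis is tied to the pre-treatment start date and almost never sees Hgb around the worsening

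*SAP*

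**What the plan says.** **Which AEs enter.** SAP Section 10.4.1.4 classifies an AE as treatment emergent "If AE onset date or AE worsening date is on or after treatment start date" and no later than one day after the last non-zero dose. Worsening has its own reference: "AE worsening during treatment emergent will be defined relative to the maximum intensity of AE prior to" the start of randomized treatment. It also has its own date: "AE worsening date is the first date in the treatment emergent period, when AE intensity increased" above that reference. AE collection begins before treatment: "Non-serious AEs and serious AEs are to be recorded on the eCRF starting at the placebo run-in phase".

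**How they are used.** Section 8.2.4 defines Tier 1 as the treatment-emergent AESIs and compares them between arms with a CMH test. Section 8.2.4.2 limits the AESI summaries to treatment-emergent AEs and lists a time to first onset or worsening among them.

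**How the erythropoiesis AESI is decided.** Section 10.6.4.4 opens the rule with the start date as its only anchor: "Thrombosis and tissue ischemia events will be considered to be secondary to excessive erythropoiesis if during the window of [AE start date". An AE on the thrombosis and ischemia term list counts only "if during the window of [AE start date – 30 days, AE start date +15 days] any one of the following 3 events occurs": Hgb of at least 13 g/dL, a rise above 2 g/dL over 2 weeks (plus 1 week), or a rise above 4 g/dL over 4 weeks (plus 1 week). To find rises, "all Hgb values taken within [AE start date – 58 days, AE start date + 15 days] will be identified". The programming rule then requires the later value of each pair to lie "within the [AE start date – 30 days, AE start date +15 days] window". The worsening date appears in none of these.

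**The concern.** An AE that is treatment emergent only because it worsened must have started before randomized treatment. The plan admits it to the treatment-emergent set because of something that happened on treatment, then judges its link to Hgb at the date of something that happened before treatment.

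The classification can go wrong in two directions:

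- An ischemic event that began in run-in and worsened on treatment with Hgb at 13 g/dL or after a steep rise would be scored as not secondary to excessive erythropoiesis. It would leave the Tier 1 count, the relative risk and the CMH comparison for this AESI.
- Prior ESA continues through screening and run-in (Section 1), so a Hgb rise near the original start could label a later, unrelated worsening as the AESI.

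At stake is the content of one nominally tested safety category.

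**Working it through.** The SAP gives no figure to reproduce. The check is date arithmetic, counted in days from treatment start (first dose = 0). The SAP's own Treatment Day (Section 10.6.1) is one higher on or after the first dose, which changes nothing of substance.

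**Inputs**

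- Hgb window: AE start −30 to +15 days; look-back for rises from −58 days (Section 10.6.4.4).
- AE recording from run-in, Week −4 (Sections 10.4.1.4 and 10.2.1.1).
- Scheduled Hgb at Week 2 (day 14 ± 3) and Week 4 (day 28 ± 3), then every 4 weeks to Week 52 (Section 10.2.1.1). This assumes treatment starts on Day 1.
- Entry Hgb 8–10 g/dL without ESA, 8–11 g/dL on ESA (Section 2.3).

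**Step 1: where the window closes.** For an AE starting at day s, the window is [s − 30, s + 15]. An AE that qualifies only by worsening has s ≤ −1, so the window closes no later than −1 + 15 = day 14. For s ≤ −15 it contains no day after the first dose.

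| AE start (s) | Window | Days after first dose in window |
|---|---|---|
| −28 | −58 to −13 | 0 |
| −21 | −51 to −6 | 0 |
| −14 | −44 to 1 | 1 |
| −7 | −37 to 8 | 8 |
| −4 | −34 to 11 | 11 |
| −1 | −31 to 14 | 14 |

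**Step 2: which scheduled on-treatment Hgb can fall inside.** A visit on day v is included only if v ≤ s + 15, that is s ≥ v − 15.

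- Week 2 at its earliest, v = 11: s ≥ −4, so start days −4 to −1 qualify, 4 of 28 run-in days (14%).
- Week 2 at its nominal day, v = 14: s ≥ −1, so only start day −1 qualifies, 1 of 28 (3.6%).
- Week 2 at its latest, v = 17: s ≥ 2, so none.
- Week 4 at its earliest, v = 25: s ≥ 10, so none. The same holds for every later visit.

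Unscheduled Hgb up to day 14 could also count, so the result is almost never, not never. With entry Hgb of at most 11 g/dL, reaching 13 g/dL needs a rise of at least 13 − 11 = 2 g/dL within about two weeks of the first dose.

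**Step 3: the same AEs with the window on the worsening date w, [w − 30, w + 15].**

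| Start | Worsening | Scheduled on-treatment Hgb, start-date window | Worsening-date window |
|---|---|---|---|
| −14 | 60 | none | day 56 |
| −20 | 100 | none | days 84, 112 |
| −28 | 200 | none | day 196 |
| −1 | 30 | day 14 | days 14, 28 |

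**Step 4: can the start date be read as including worsening?** Section 10.4.1.4 lists the two dates on separate lines for each post-treatment-start state, and Section 10.7.2.1 sets an imputed worsening date to the start date when it would fall earlier. They are different variables, so a literal program would use the original start.

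**The case against.** **The anchor could be deliberate.** The category concerns what caused the event, and an event that began before the first dose was not started by on-treatment Hgb. Other AESIs in the same list name deterioration outright (hypertension, rheumatoid arthritis, tumor progression); this one does not. That is a fair reading of the label, but it does not explain the rule. The plan keeps worsened AEs in the treatment-emergent set from which Tier 1 is drawn, and then tests them on Hgb from a period largely before the study drug could act. Had the intention been to exclude them, the plan would have to say so; as written they can still qualify, on the wrong Hgb.

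**The size could be overstated.** This objection stands. A reader might apply an assumed rate such as 0.1–0.5% of the 4,500 planned subjects and infer about 5 to 22 lost events. The documents give no such rate, and that product would count worsenings, not misclassifications. Dosing targets Hgb of 10–11 g/dL, so many worsenings would fail the Hgb criteria under either anchor and are correctly excluded.

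**The events are not lost from reporting.** This also stands. They remain in the treatment-emergent AE tables and, if serious, in the SAE tables (Section 8.2.4.2). MI, stroke and thromboembolic endpoints are adjudicated separately with their own dates (Section 10.6.4.1). The rule is the same in both arms, and no direction of bias between arms is shown.

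**A simple swap of dates would be incomplete.** Section 10.4.1.4 defines several worsening dates, so the fix must name one. AEs that start on treatment and worsen later would still be judged at onset. For them, though, the start date is itself the event that made the AE treatment emergent, so the mismatch described here does not arise.

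**Conclusion.** The point holds as a definitional mismatch between Sections 10.4.1.4 and 10.6.4.4. For thrombosis and ischemia AEs that are treatment emergent only through worsening, the Hgb test closes no later than 14 days after the first dose and almost never covers the worsening. A worsening that meets a Hgb criterion would then usually be left out of the Tier 1 AESI, and the opposite error is also possible.

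The size is not given in the document, is likely small and may be zero. A misclassified omission needs a listed term, onset before treatment, an AE still open, intensity above its pre-treatment maximum while treatment emergent, and a Hgb criterion met near the worsening. The period concerned ends one day after the last non-zero dose, not at study end.

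It would be tempting to infer a serious flaw in the Tier 1 analysis or a bias between arms. The documents support neither: one AESI is involved, it is tested without multiplicity control, and no co-primary or principal secondary analysis depends on it. The conclusion rests on reading the AE start date literally and on treatment starting on Day 1. This is a minor correction worth making.

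**What to change.** In Section 10.6.4.4, state that for AEs that are treatment emergent through worsening, both Hgb windows (−30/+15 and −58/+15 days) and the pairwise programming rule for rises use the treatment-emergent AE worsening date as defined in Section 10.4.1.4. Name that date explicitly, because the same section defines others for run-in, post-randomization and follow-up. Keep the AE start date for AEs whose onset is on treatment. The Hgb thresholds do not change.

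The cost is a sentence in the SAP and a small change to the derivation program. The worsening date is already defined in the SAP, so no new data are needed.

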8.2.4. Adverse Event Safety Analyses

Adverse events will be coded using the Medical Dictionary for Regulatory Activities (MedDRA) coding dictionary.

The reporting of the CEC-adjudicated CV endpoint events has been described in Section 7.2, Section 8.2.1 and Section 8.2.2. However, AE summaries and analysis will also include the AEs and SAEs associated with the adjudicated events listed below:

- All-cause mortality (CV and non-CV mortality)
- Non-fatal MI
- Non-fatal stroke
- Hospitalization for HF
- Thromboembolic events (vascular access thrombosis, deep vein thrombosis, pulmonary embolism)
- Progression of CKD

For the purpose of AE summaries and analysis, the investigator-reported AE details will be used, regardless of the adjudication outcome of the event.

Adopting recommendations from the Pharmaceutical Research and Manufacturers of America (PhRMA) Safety Planning, Evaluation and Reporting Team (SPERT) [Crowe, 2009], the first two tiers of the three-tier system will be used for the evaluation of AEs to examine the level of statistical evidence for differences between treatment groups.

- Tier 1 events in this study are defined as treatment emergent AEs of special interest (AESI). Tier 1 events will include AEs which meet criteria for inclusion as an AESI (see Section 10.6.4). Statistical comparisons will be made to compare the number and % of AESIs between the treatment groups, using the CMH chi-square test. A nominal statistical association will be declared if the unadjusted two-sided p-value for an event is less than 0.05.
- Tier 2 events in this study are defined as the most common treatment emergent AEs (those occurring in $\geq 5\%$ of subjects in any treatment group). Tier 2 events are mutually exclusive of the Tier 1 AESI events. Any statistical comparisons for Tier 2 events will be made to compare treatment groups with multiplicity adjustment, using a CMH chi-square test, and the double false discovery rate (FDR, see Section 10.6.4) [Mehrotra, 2012]. The double FDR multiplicity procedure is designed to limit the number of false positive signals identified to no more than two-sided 10% (the false discovery rate).

Unless otherwise specified, all other AE and SAE summaries will include all AEs.

See Section 10.4.1 for AE treatment state definitions.

The adverse event safety analyses will be based on the Safety population, unless otherwise specified.

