10.6.3. Efficacy

10.6.3.1. Hemoglobin Endpoints

Hemoglobin Values
Central Laboratory and HemoCue Hgb Values

 ● When source of Hgb measurement is not specified: 
 ○ For reporting purposes, central laboratory Hgb values will be used, unless otherwise specified. However, if a central laboratory Hgb value is missing, a corresponding non-missing HemoCue Hgb value will be used. This approach will

Hemoglobin Values

be used for the co-primary Hgb analysis.
 
 Some displays may be created for either central laboratory Hgb values only or HemoCue Hgb values only. The central laboratory summary will be considered the primary summary in this case.
Evaluable Hemoglobin Values

 Evaluable Hgb values are on-treatment Hgb values (see Section 10.4.1) that are not taken within the 8 weeks following a red blood cell transfusion, a whole blood transfusion, or a non-randomized ESA treatment which occurs on or after the randomization date. Red blood cell transfusions, whole blood transfusions and non-randomized ESA treatments occurring on or after the randomization date are identified by comparing the start and stop date of the respective transfusion or ESA concomitant medication record to the randomization date.
Imputed Hemoglobin Values

 For each missing value between baseline to Week 52 (inclusive), 200 imputed values will be generated using the multiple imputation method (see Section 7.1.2). The average of these 200 imputed values will be used as the value for this missing value in the summary tables and figures. For co-primary efficacy Hgb analysis and the corresponding subgroup analyses using all available observed and imputed Hgb values (on and off-treatment), Rubin's rules [Rubin, 1987] will be used to combine results of the imputed datasets using SAS PROC MIANALYZE procedure.
EP Hemoglobin Value for Co-primary Hgb Analysis

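### The Hgb step for the thrombosis/tissue ischemia AESI counts a qualifying rise whatever its cause, including a transfusion at or after the event, and its 58-day look-back is a week short of its own 5-week comparison

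*SAP*

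**What the plan says.** Section 10.6.4.4 first selects adverse events by preferred-term lists. For the thrombosis/tissue ischemia category it then applies Hgb criteria, with the stated aim of retaining only events secondary to excessive erythropoiesis. An event is retained "if during the window of [AE start date – 30 days, AE start date +15 days] any one of the following 3 events occurs": an Hgb of at least 13 g/dL, a rise above 2 g/dL over 2 weeks (+1 week), or a rise above 4 g/dL over 4 weeks (+1 week).

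For the two rise criteria the section gives a programming rule:

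- **Values retrieved.** "To identify Hgb increases that meet the increase criterion above, all Hgb values taken within" a span from 58 days before to 15 days after AE start. The SAP explains 58 days as reaching 4 weeks before the 30-day window.
- **2 g/dL comparison.** "Between 1 day and 3 weeks, inclusive, then the Hgb values will be compared to determine if there has been a Hgb increase" above 2 g/dL.
- **4 g/dL comparison.** "Between 15 days and 5 weeks, inclusive, then the Hgb values will be compared to determine if there has been a Hgb increase" above 4 g/dL.
- **Sources.** HemoCue and central laboratory values are assessed separately. Unscheduled values are used, and Section 10.6.3 is invoked only for unscheduled values and several values on one date.

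Section 10.6.3.1 defines evaluable Hgb as on-treatment values "that are not taken within the 8 weeks following a red blood cell transfusion", a whole blood transfusion or a non-randomized ESA. Section 10.6.4.4 does not call that definition.

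Under Sections 8.2.4 and 8.2.4.2, treatment-emergent AESIs are Tier 1 events, compared by a CMH test at an unadjusted two-sided 0.05, with relative risk and 95% CI.

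**The concern.** The step exists to separate events plausibly due to excessive erythropoiesis from other thrombotic or ischemic events, but it has no condition on the cause of the rise. Transfused red cells raise Hgb without erythropoiesis, and the SAP treats transfusion as distorting Hgb when it defines evaluable values. Because the window runs to 15 days after AE start, and the only ordering required is that one value precede the other, both values of a pair may follow the event. A patient who is transfused around an ischemic event can then be classed as having had an event secondary to excessive erythropoiesis.

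The look-back raises a separate, purely internal inconsistency. The one-week visit tolerance was added to the comparison interval but not to the retrieval window, so some pairs that the comparison rule allows are never retrieved.

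At stake is how specific this AESI is, and hence how the Tier 1 relative risk for it can be read.

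**Working it through.** **1. Does a transfusion-driven rise qualify?** The SAP gives no figure to reproduce, so the rule was applied literally to assumed Hgb series (days relative to AE start).

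| Assumed series (g/dL) | Transfusion | Largest rise within 21 days | As written | Pairs spanning a transfusion dropped |
|---|---|---|---|---|
| 9.8 (day −14), 7.2 (day 0), 9.5 (day 7) | day 1 | 9.5 − 7.2 = 2.3 in 7 days | flagged | not flagged |
| 7.4 (day 2), 9.6 (day 10) | day 5 | 9.6 − 7.4 = 2.2 in 8 days | flagged | not flagged |
| 9.8 (day −14), 9.6 (day 0), 9.7 (day 7) | none | 9.7 − 9.6 = 0.1 | not flagged | not flagged |
| 9.0 (day −14), 9.2 (day 0), 10.5 (day 7) | none | 10.5 − 9.0 = 1.5 | not flagged | not flagged |

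The second series lies wholly after the event. The last two show that smaller movements do not count.

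**2. How often could such a pair arise?** By the schedule in Section 10.2.1.1:

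- Visits from Week 4 to Week 52 are nominally 28 days apart, with a window of ±7 days (±3 at Week 4). Two consecutive scheduled visits fall within 21 days only when their timing shortens the gap by at least 7 days.
- From Year 2, visits are 84 days apart, so consecutive ones are at least 84 − 14 = 70 days apart.

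Many pairs within 3 weeks therefore need an unscheduled study visit. Frequency cannot be derived further from the SAP.

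**3. Direction of the effect on the relative risk.** Let f be the share of darbepoetin alfa AESIs that are spurious, with the same absolute spurious rate in both arms. Then observed RR = RR × (1 − f) + f. No rate in the SAP fixes f, so a range is shown:

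| True RR | f = 10% | 20% | 30% | 50% |
|---|---|---|---|---|
| 1.5 | 1.45 | 1.40 | 1.35 | 1.25 |
| 2.0 | 1.9 | 1.8 | 1.7 | 1.5 |

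For example, 1.5 × 0.8 + 0.2 = 1.40. If transfusion use around events differs between the open-label arms, the equal-rate assumption fails and the bias can go either way.

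**4. The look-back.**

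- The later value may lie as early as day −30, and the comparison interval reaches 35 days. Required look-back: 30 + 35 = 65 days. Stated: 30 + 28 = 58 days.
- A pair is lost when (days from later value to AE) + (interval) exceeds 58. With interval at most 35, the later value must be at least 59 − 35 = 24 days before the AE. With the later value at most 30 days before it, the interval must be at least 59 − 30 = 29 days. So the exposed pairs are 29–35 days apart with the later value 24–30 days before the AE. Example: values on days −62 and −30 are 32 days apart, yet day −62 is not retrieved.
- The 2 g/dL criterion is unaffected, since 30 + 21 = 51 is below 58.
- The later value is itself inside the 13 g/dL window. If the earlier Hgb is 9 g/dL or more, a rise above 4 g/dL takes it past 13 and the event is retained anyway. Only pairs starting below 9 g/dL can be missed, and only if no other criterion is met.

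**The case against.** The strongest case against has four parts.

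**Few qualifying pairs.** The rule names only HemoCue and central laboratory values and never mixes them, so hospital laboratory readings taken around an admission are not a stated source. The schedule footnotes also say hematology samples are not required at the additional visits that check Hgb. This stands. It limits the number of events affected but does not change what the rule does with pairs that exist.

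**Little consequence from 58 days.** The 13 g/dL criterion already catches most exposed pairs. This stands too, and leaves an inconsistency with a narrow effect.

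**Limited weight.** The Tier 1 test is nominal and outside the confirmatory family of Section 10.11.1.2, and the cumulative incidence plot is optional. A reader might infer that the trial's thrombotic safety conclusions are compromised. The SAP does not support that: adjudicated MACE, MACE or thromboembolic events, and the separate MI, stroke and thromboembolic analyses use no Hgb filter. Nor does it support a claim that the Tier 1 relative risk is materially distorted, because it contains no rates from which to judge.

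**Sensitivity.** A broad safety algorithm may be preferred, since excluding pairs that span a transfusion also removes events to which drug and transfusion both contributed. This is a fair cost, and it is met by also reporting the AESI without the exclusion. It does not make the broad version conservative for a comparison of arms, because equal false positives pull the relative risk toward 1.

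**Conclusion.** The point holds in a limited form. As written, Section 10.6.4.4 retains qualifying rises of any cause, including one explained by a transfusion at or after the event, and so does not achieve its stated aim of keeping only events secondary to excessive erythropoiesis. It does not count every rise: the 2 and 4 g/dL thresholds, the time limits and the single-method requirement all apply.

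The number of misclassified events is unknown and probably small, and the effect stays within one nominal Tier 1 comparison. The direction toward 1 rests on equal spurious rates in the two arms; the dilution figures rest on assumed values of f.

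The 58-day look-back contradicts the 5-week comparison by arithmetic alone. Its practical reach is confined to rises above 4 g/dL from below 9 g/dL that meet no other criterion.

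**What to change.** In Section 10.6.4.4:

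1. State that a rise is not counted when a red-cell or whole-blood transfusion was given between the earlier and the later Hgb value, and say how same-day dates are handled. Leave the 13 g/dL criterion and the 15-day limit unchanged.
2. Report the AESI without this exclusion as a sensitivity display.
3. Change the look-back from 58 to 65 days in both places where it appears, and the accompanying explanation from 4 to 5 weeks.

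This is narrower than importing the evaluable-Hgb definition, which would also drop off-treatment values and values after a non-randomized ESA.

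The cost is a few lines of SAP text, one programming condition on transfusion dates already collected, and one extra display. Slightly fewer events will be classed as this AESI, including some where drug and transfusion both contributed; the sensitivity display keeps those visible.
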